5.2 Safety Population

Safety analysis set is a set of subjects to whom the IMP has been administered, and who had 1 or more evaluable, post-IMP administration safety data points. Safety endpoints include adverse events, laboratory values, vital signs, weight, physical examination, standard 12-lead ECG, neurological symptoms and blood CD4⁺ cell count. Patients in the safety population will be analyzed according to the treatment actually received at remission-induction period.

5.3 Pharmacokinetic Analysis Set

The **pharmacokinetic analysis set** will be defined as all available data on patients who took the active treatment and who had 1 or more evaluable, post-IMP serum E6011 concentration data points.

5.4 Pharmacodynamic Analysis Set

The **pharmacodynamic analysis set** will be defined as all available data on patients who took the active treatment and who had 1 or more evaluable, post-IMP PD biomarker data points.

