# 9.7.1.2 Definition of the analysis population

FAS (full analysis set) is a set of subjects to whom the IMP has been administered after randomisation, and who had 1 or more evaluable, post-IMP administration primary efficacy endpoint data points.

PPS (per protocol set) is a set of subjects who satisfactorily complied with the Protocol. Detailed

criteria deemed to match present analysis sets are to be decided upon before the database is locked and unblinded, and they are to be specified in the analysis plan.

Safety analysis set is a set of subjects to whom the IMP has been administered, and who had 1 or more evaluable, post-IMP administration safety data.

Pharmacokinetic analysis set is a set of subjects to whom the IMP has been administered, and who had 1 or more evaluable, post-IMP administration serum E6011 concentration data points.

Pharmacodynamic analysis set is a set of subjects to whom the IMP has been administered, and who had 1 or more evaluable, post-IMP administration biomarker data points.

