For Week 12 CR100 rate, the Bayesian posterior distribution of the difference in the CR100 rate at Week 12 between the E6011 group and the placebo group is to be calculated. If there was a 50% or more probability of the difference between both groups being 25% or more, the efficacy of E6011 is confirmed. Noninformative prior distribution is to be used for both the E6011 group and the placebo group.

Subjects with missing primary endpoint data by Week 12 after administration due to premature discontinuation or other reasons are treated as treatment failures (non-responder imputation [NRI]).

Analysis of secondary endpoints

- CDAL response rate (CR70, CR100 (excluding Week 12)) and remission rate are to be calculated by treatment group and evaluation time. Summary statistics for CDAL value, change and percent change from baseline are also to be calculated by treatment group and evaluation time.
- PRO2 response rate (PRO2-CR5, PRO2-CR8) and remission rate are to be calculated by treatment group and evaluation time. Summary statistics for PRO2 value, change and percent change from baseline are also to be calculated by treatment group and evaluation time.
- SES-CD endoscopic response rate and endoscopic remission rate are to be tabulated by treatment group and evaluation time. Summary statistics for SES-CD value, change and percent change from baseline are also to be calculated by treatment group and evaluation time.
- Steroid-free remission rate and steroid-free response rate in subjects concomitantly using adrenocorticosteroids is to be tabulated by treatment group and evaluation time. Summary statistics for steroid dosage, change and percent change from baseline are also to be calculated for each treatment group and evaluation time.

Pharmacokinetics

Drug concentration is to be analyzed using the drug concentration analysis set. Summary statistics for serum E6011 concentration are to be calculated for each specified time. Serum E6011 concentration-time profile is also to be created.

Biomarkers, pharmacogenomics/pharmacogenetics

Biomarkers, pharmacogenomics/pharmacogenetics are to be analyzed using the pharmacodynamic analysis set. Summary statistics for serum total FKN concentration, faecal calprotectin and serum CRP concentration measured values, change and percent change from baseline are to be calculated by treatment group and evaluation time. CCI

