2. LIST OF ABBREVIATIONS

Abbreviations	Unabbreviated Terms (English)
BMI	Body mass index
CI	Confidence Interval
CDAI	Crohn's disease activity index
CRP	C-reactive protein
CV	Coefficient of variation
eCRF	electronic Case Report Form
FAS	full analysis set
FKN	Fractalkine
ICH	International Council for Harmonisation of Technical Requirements for Pharmaceuticals for Human Use
IMP	Investigation Medical Product (or Placebo)
JCV	JC virus
LLOQ	Lower Limit of Quantification
LOCF	Last Observation Carried Forward
MCMC	Markov chain Monte Carlo
MedDRA	medical dictionary for regulatory activities
MI	Multiple Imputation
OC	Observed Case
PD	Pharmacodynamics
PK	Pharmacokinetics
PML	progressive multifocal leukoencephalopathy
PPS	Per Protocol Set
PT	preferred term
SAP	Statistical Analysis Plan
SES-CD	simple endoscopic score for Crohn's disease
SD	Standard deviation
SOC	system organ class
TEAE	treatment emergent adverse events
WHO DD	world health organization drug dictionary

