- 2) Rescue Period (Open label): comprises from week 12 to week 24 for non-responders. Subjects with a reduction in the CDAI of less than 70 compared to baseline after finishing evaluation in Week 12 of the remission-induction period are to move on to the rescue period. The rescue period is to last 12 weeks, with 10 mg/kg of E6011 administered in an unblinded manner on Week 12, Week 13, Week 14 and every two subsequent weeks until Week 22.
- 3) Extension Period (Open label): comprises from week 12 to week 52 for responders at week 12 and from week 24 to week 64 for non-responders at week 12. Subjects who

finished evaluation at Week 12 of the remission-induction period and had a CDAI response of 70 or more, and subjects who moved on to the rescue period and finished evaluation at Week 24 with a CDAI response of 70 or more are to move on to their respective extension period. The extension period is to last 40 weeks, with 10 mg/kg E6011 administered in an unblinded manner every four weeks up to Week 48(responders) or Week 60(non-responders).

- 4) Post-Observation Period: After the extension period of the clinical trial has been finished or discontinued, examinations are to be carried out 28 days after the completion or discontinuation of the extension period and 70 days after the last administration of the IMP.
- 5) Follow-up Period: PML onset is to be investigated over the phone, etc. every 6 months in the two-year follow-up period after the last IMP administration.

Four analysis periods are defined:

- 1) Remission-induction period: as defined above.
- 2) Rescue period: as defined above. This period will be used only for adverse events endpoints.
- 3) Entire administration period comprises the remission-induction period, the rescue period, the extension period and the post-observation period as defined above.
- 4) Follow-up period: as defined above.

Analyses of the remission-induction period will be performed after the remission-induction period is completed. Analyses of the entire administration period (remission-induction period, rescue period, extension period and post-observation period) will be performed after the post-observation period is completed. Analysis of the follow-up period will be performed after the follow-up period is completed.

In all TFLs that are displayed by treatment groups they will refer to the remission-induction treatments.

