6.10.3 Biomarker and Pharmacogenomic Parameters

Exploratory biomarker and pharmacogenomic analyses are to be performed using the pharmacodynamic analysis set. Summary statistics for serum total FKN concentration, measured faecal calprotectin and serum CRP levels, change and % change from baseline are to be calculated by treatment group and evaluation time.

CCI

Details and results of the analysis of blood CD16⁺ monocytes, etc. and blood CD16⁺ monocytes etc. genetic markers are to be reported in a separately created report, and not included in the Clinical Study Report

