10 GENERAL FORMAT OF TABLES, FIGURES AND SUBJECT DATA

Tables and listings will be produced in accordance with the principles outlined by the ICH E3 guideline. All summary tables will be presented by treatment group and race (all, Japanese and non-Japanese).

The design of the tables will be clear and concise so that comparative reading is easily possible.

All descriptive variables will be tabulated. Quantitative variables will be described showing their number of available and missing observations, mean and its CI (95% level), median, standard deviation, the range (minimum and maximum) and the first and third quartiles. Frequency and percentage will describe qualitative variables.

Missing values will be tabulated with their frequency but will not be included in the calculation of percentages. Analysis will be based on observed cases, i.e., no replacement of missing data is planned in general except otherwise planned in the appropriate statistical methodology section (section 11, section 12 or 14).

Pharmacokinetic data (E6011 serum concentrations) will be summarized by treatment group and race (All, Japanese and Non-Japanese) and evaluation time, including the number of sample results, minimum, medium, maximum, mean, standard deviation and coefficient of variation (CV). In addition, geometric means and geometric CV will be also shown.

Serum E6011 concentration vs time curves will be prepared. A serum concentration profile will be prepared for each subject and shown individually on a single plot per patient. A plot showing all serum profiles generated per treatment group will be prepared.

Summary serum E6011 concentration vs time profiles will also be prepared. A geometric mean serum profile will be shown by treatment group individually and grouped by treatment.

Pharmacodynamic data (serum total FKN concentrations, faecal calprotectin and serum CRP concentration measured values, change and % change from baseline) will be summarized by treatment group, evaluation time and race (all, Japanese and non-Japanese), including the number of sample results, minimum, medium, maximum, mean, standard deviation and coefficient of variation (CV). In addition, geometric means and geometric CV will be also shown.

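### SAP 5.4 requires active treatment for the pharmacodynamic set, so it departs from the protocol and leaves unclear which placebo patients enter the by-arm biomarker tables

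*SAP*

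**What the plan says.** The two documents define the pharmacodynamic (PD) set differently.

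- **Protocol 9.7.1.2 (version 11.0):** "Pharmacodynamic analysis set is a set of subjects to whom the IMP has been administered", with at least one evaluable biomarker value afterwards. Protocol 9.5.1.5.1 states that IMP means both E6011 and placebo, and the SAP's abbreviation list expands IMP as "Investigation Medical Product (or Placebo".
- **SAP 5.4:** the set is "defined as all available data on patients who took the active treatment and who had 1 or more evaluable, post-IMP PD biomarker data points".

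The SAP then uses this set for comparisons by arm.

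- **SAP 6.10.3:** "Exploratory biomarker and pharmacogenomic analyses are to be performed using the pharmacodynamic analysis set".
- **SAP synopsis:** "faecal calprotectin and serum CRP concentration measured values, change and percent change from baseline are to be calculated by treatment group and evaluation time".
- **SAP 10:** PD data, including "change and % change from baseline) will be summarized by treatment group, evaluation time and race".
- **SAP 6.1:** "In all TFLs that are displayed by treatment groups they will refer to the remission-induction treatments". The columns are therefore E6011 and placebo as given in Weeks 0 to 12.

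Two neighbouring definitions have similar wording. SAP 5.3 limits the pharmacokinetic (PK) set to "patients who took the active treatment and who had 1 or more evaluable, post-IMP serum E6011 concentration data points". SAP 4.1 ties the general baseline to the first E6011 injection, not to the first IMP administration.

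**The concern.** A table by randomised arm needs a set that contains both arms. SAP 5.4 makes entry depend on having taken active treatment, and a placebo patient can meet that condition only after Week 12, if at all.

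This matters most for FKN, the target of E6011. FKN is sampled only in the remission-induction period (Weeks 0 to 12 and at discontinuation), so the blinded placebo arm is its only concurrent comparator. Calprotectin continues after Week 12, but everyone still on treatment then receives E6011, so its controlled comparison is also confined to Weeks 0 to 12.

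At stake is whether the placebo column in those summaries is complete, is selected by what happened after randomisation, or is missing. As SAP 5.4 stands, two programmers could build different sets in good faith.

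**Working it through.** The plan gives no figure on this point, so the check is a comparison of texts followed by a simple count.

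**1. Is the active-treatment condition just another way of saying IMP?** No. The sentence in SAP 5.4 uses both terms, and SAP 5.1 and 5.2 define the efficacy and safety sets by IMP. The active-treatment condition is an added restriction.

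**2. Who is in the set under each definition?** Every patient below is assumed to have at least one evaluable biomarker value after IMP. Under Protocol 9.1, both responders and non-responders at Week 12 start open-label E6011.

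| Patient | Protocol 9.7.1.2 | SAP 5.4, by randomised arm | SAP 5.4, ever given E6011 |
|---|---|---|---|
| E6011, reaches Week 12 | in | in | in |
| E6011, stops early | in | in | in |
| Placebo, starts E6011 at Week 12 | in | out | in |
| Placebo, stops before any E6011 | in | out | out |

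Neither SAP reading reproduces the protocol column. The by-arm reading also conflicts with SAP 6.10.3, 10 and 6.1, which call for a placebo column. The ever-exposed reading keeps that column but treats early stoppers differently in the two arms.

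**3. Inputs for size.**
- 25 subjects enrolled (Protocol 9.7.2) and 1:1 allocation (Protocol 9.1). The actual split is not given, so 12 or 13 on placebo is assumed.
- Early stopping before Week 12: the documents give no rate, so 0 to 20% is assumed.
- Induction visits (SAP 6.6.2): FKN at Weeks 0, 1, 2, 4, 6, 8, 10 and 12, which is 8; calprotectin at Weeks 0, 2, 4, 8 and 12, which is 5.

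**4. Ever-exposed reading.** Placebo patients lost = stopping rate × placebo patients.
- At 0%: none.
- At 20%: 0.20 × 12 = 2.4, or 0.20 × 13 = 2.6.
- Range: 0 to about 3 of 12 or 13.

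**5. By-arm reading.** All placebo samples leave the summaries. For the induction period, with full attendance and Week 0 counted:
- FKN: 12 × 8 = 96 or 13 × 8 = 104, out of 25 × 8 = 200 (48% or 52%).
- Calprotectin: 12 × 5 = 60 or 13 × 5 = 65, out of 25 × 5 = 125 (48% or 52%).

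These percentages are simply the placebo share of patients (12/25 or 13/25). They show what an empty column would mean and do not predict that it will occur.

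**The case against.** The best defence is that SAP 5.4 refers to patients who took active treatment, not to patients randomised to it, and that it admits all their available data. Placebo patients who reach Week 12 do go on to E6011, so they qualify with their Week 0 to 12 values. The SAP plainly expects a placebo column. On that view only a few early placebo stoppers are lost, from descriptive summaries that SAP 6.10.3 calls exploratory. SAP 4.10 also lists individual FKN, calprotectin and CRP values without confining the listing to the PD set, and SAP 6.9.2 tabulates CRP by treatment in the safety population.

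All of this stands, and it limits the point. It does not remove it: the favourable reading still departs from Protocol 9.7.1.2, still selects placebo patients on a post-randomisation event, and is not the only way to read the sentence.

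Four stronger inferences are tempting, and the documents do not support them.

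- *The placebo column is certainly empty.* That follows from only one of two readings, and the SAP's by-arm tables speak against it.
- *SAP 4.1 gives placebo patients a Week 12 baseline and so distorts the primary endpoint.* Taken literally, a placebo patient's first E6011 comes at Week 12. But SAP 4.1 itself says that assessments precede IMP, SAP 6.6 places the baseline visit at day 1, Protocol 9.1 and inclusion criterion 3 place it at Week 0, and SAP 6.8.2 tabulates change from baseline up to Week 12. It is a slip that no analyst would follow.
- *SAP 6.11 is false in declaring no modifications.* SAP 6 is written against protocol version 10, and the protocol supplied is version 11.0. Whether 6.11 was right against version 10 cannot be settled here.
- *The PK set in SAP 5.3 is an equal fault.* The analyte there is the drug itself, so an active-only set is unremarkable. SAP 6 also sends the PK objectives to a separate analysis plan that was not supplied.

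**Conclusion.** The concern holds as a minor inconsistency in the definition of an analysis set. SAP 5.4 conflicts with Protocol 9.7.1.2 (version 11.0) on either reading, and on the by-arm reading it also conflicts with the SAP's own tables. No other passage resolves it.

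The likely practical effect is small, within the range in step 4 of the working, and that range rests on the assumed arm split and stopping rate. The larger loss in step 5 applies only if the set is built by randomised arm. The direction of any bias from losing early placebo stoppers cannot be determined from the documents.

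No decision rule, sample size or error rate is affected. What is exposed is the descriptive placebo comparison for FKN and calprotectin, and for CRP only in its PD presentation. No numerical effect is claimed for the SAP 4.1 wording.

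**What to change.** **Main change.** In SAP 5.4, put back the definition in Protocol 9.7.1.2: all subjects given IMP, whether E6011 or placebo, who have at least one evaluable biomarker value after IMP administration.

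**Tidy-ups.**
- SAP 4.1: refer the baseline to the first administration of IMP at Week 0, and name IMP in the definition of change from baseline, which mentions dosing without saying of what.
- SAP 5.3: if the active-only PK set is kept, check it against protocol version 10 and the separate PK analysis plan, and record any difference in SAP 6.11.

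**Cost.** Three wording edits (one in 5.4, two in 4.1) and possibly one line in 6.11. No new data are needed, and neither the sample size nor the primary analysis changes.

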5.5 Immunogenicity Analysis Set

The immunogenicity will be analyzed using the safety analysis set.

6 STATISTICAL METHODOLOGY

This analysis plan gives a detailed description of the statistical methodologies, data listings, summary tables, and figures planned in the analyses of the data in the E6011-ET2 study.

This section describes the statistical analyses of the study based on the statistical section of the English protocol v10 17SEP2021. Any differences with the protocol will be identified and documented.

The statistical data analyses, described in this document, are intended to provide unbiased and valid conclusions concerning the objectives of the study.

This SAP describes only the analyses for the study objectives not involving the pharmacokinetic objectives. These will be described in a separate analysis plan.

6.1 General Methods

The analysis of the present study will be exploratory and primarily make use of descriptive statistical methods. In addition, exploratory statistical testing and modelling will be used to highlight interesting aspects of the data.

The continuous variables will be summarized using the following descriptive statistics:

- Number of patients (Number)
- Mean
- Standard deviation (SD)
- Median
- Minimum (min)
- Maximum (Max)
- Quartile 1 (Q1)
- Quartile 3 (Q3)
- Number of missing data (Missing)

Changes from baseline will be presented with its 95% confidence intervals.

For categorical variables including binary variables, the absolute (n) and relative frequency (%) will be summarized for each category at each scheduled visit.

All tables will be summarized by Japanese race.

Additionally, when appropriate, tables of efficacy endpoints (CDAI, PRO2 and SES-CD) in the remission-induction period will be summarized by:

- Sex: Male; Female
- Age: <35, 35-<50, ≥50
- Previous biologics: Yes; No.
- Prior biologic treatment used of Crohn's disease: Biologic naïve; 1 prior biologic failure; 2 prior biologic failures; ≥3 prior biologic failures
- CD-Type: Small intestine-type; Large intestine-type; Small and large intestine-type.
- CD duration: ≤5 years; > 5 years.
- CD-related surgery: Yes; No.
- Corticosteroids concomitant before randomization : Yes; No.
- Immunomodulators concomitant before randomization : Yes; No.
- Enteral nutrition concomitant before randomization : Yes; No.
- Baseline CDAI: ≤330; > 330.
- Baseline PRO2: ≤24; > 24.
- Baseline SES-CD: ≤15; > 15.

If one of the subgroups above has less than 5 patients, no results will be displayed.

Tables for adverse events in the remission-induction period will be summarized by:

- Sex: Male; Female
- Proclivity to hypohepatia: Yes, No
- Baseline eGFR: <30, 30-<60, 60-<90, ≥90

Five periods are defined in the study:

- 1) Remission-Induction Period (blind): comprises from day 0 to week 12. Subjects who were deemed eligible to participate in the screening period and at baseline are to be allocated to the E6011 10 mg/kg group and placebo group at the ratio of 1:1 using stratified allocation in which race and history of previous use of biologics are used as allocation factors. E6011 or placebo is to be administered to allocated subjects in a double-blind method on Week 0, Week 1, Week 2, and every two subsequent weeks until Week 10.
- 2) Rescue Period (Open label): comprises from week 12 to week 24 for non-responders. Subjects with a reduction in the CDAI of less than 70 compared to baseline after finishing evaluation in Week 12 of the remission-induction period are to move on to the rescue period. The rescue period is to last 12 weeks, with 10 mg/kg of E6011 administered in an unblinded manner on Week 12, Week 13, Week 14 and every two subsequent weeks until Week 22.
- 3) Extension Period (Open label): comprises from week 12 to week 52 for responders at week 12 and from week 24 to week 64 for non-responders at week 12. Subjects who

finished evaluation at Week 12 of the remission-induction period and had a CDAI response of 70 or more, and subjects who moved on to the rescue period and finished evaluation at Week 24 with a CDAI response of 70 or more are to move on to their respective extension period. The extension period is to last 40 weeks, with 10 mg/kg E6011 administered in an unblinded manner every four weeks up to Week 48(responders) or Week 60(non-responders).

- 4) Post-Observation Period: After the extension period of the clinical trial has been finished or discontinued, examinations are to be carried out 28 days after the completion or discontinuation of the extension period and 70 days after the last administration of the IMP.
- 5) Follow-up Period: PML onset is to be investigated over the phone, etc. every 6 months in the two-year follow-up period after the last IMP administration.

Four analysis periods are defined:

- 1) Remission-induction period: as defined above.
- 2) Rescue period: as defined above. This period will be used only for adverse events endpoints.
- 3) Entire administration period comprises the remission-induction period, the rescue period, the extension period and the post-observation period as defined above.
- 4) Follow-up period: as defined above.

Analyses of the remission-induction period will be performed after the remission-induction period is completed. Analyses of the entire administration period (remission-induction period, rescue period, extension period and post-observation period) will be performed after the post-observation period is completed. Analysis of the follow-up period will be performed after the follow-up period is completed.

In all TFLs that are displayed by treatment groups they will refer to the remission-induction treatments.

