#### 9.7.1.6.2 Analysis of secondary efficacy endpoints

- CDAI response rate [CR70, CR100 (excluding Week 12)] and remission rate are to be calculated by treatment group and evaluation time. Summary statistics for CDAI value, change and percent change from baseline are also to be calculated by treatment group and evaluation time.
- PRO2 response rate (PRO2-CR5, PRO2-CR8) and remission rate are to be calculated by treatment group and evaluation time. Summary statistics for PRO2 value, change and percent change from baseline are also to be calculated by treatment group and evaluation time.
- SES-CD endoscopic response rate and endoscopic remission rate are to be calculated by treatment group and evaluation time. Summary statistics for SES-CD value, change and percent change from baseline are also to be calculated by treatment group and evaluation time.
- Steroid-free remission rate and steroid-free response rate in subjects concomitantly using adrenocorticosteroids is to be tabulated by treatment group and evaluation time. Summary statistics for steroid dosage, change and percent change from baseline are also to be calculated for each treatment group and evaluation time.

Subjects with missing secondary endpoint data due to premature discontinuation before 12 weeks after administration or other reasons are treated as non-responders (NRI) in the analysis of secondary endpoints.

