4.5.2 Secondary Endpoints for Efficacy

- CR70 response rate, CR100 response rate (excluding Week 12) and CDAI remission rate (proportion of subjects with below 150 points) at each evaluation time
- Proportion of subjects with at least 5-point reduction in PRO2 from baseline (PRO2-CR5 response rate), proportion of subjects with at least 8-point reduction from baseline (PRO2-CR8 response rate), and proportion of subjects with below 8 points (PRO2-remission rate) at each evaluation time
- Proportion of subjects with at least 50% improvement in SES-CD score from prior to IMP administration (endoscopic response rate) and proportion of subjects with 2 or less in SES-CD score (endoscopic remission rate) at Week 12
- Change and percent change in CDAI score from baseline at each evaluation time
- Change and percent change in PRO2 from baseline at each evaluation time
- Change and percent change in SES-CD score from baseline at Week 12
- In subjects who were concomitantly taking adrenocorticosteroid at remission induction period, proportion of subjects who achieved steroid-free maintenance (steroid-free remission rate, steroid-free improvement rate) through steroid dose reduction and clinical remission (CDAI remission or PRO2 remission) or clinical improvement (CR70 response, CR100 response, PRO2-CR5 response or PRO2-CR8 response)
- In subjects who were concomitantly taking adrenocorticosteroid at remission induction period, dosage (mg/day), change and percent change of adrenocorticosteroid from baseline.

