6.8.2 Secondary Efficacy analysis

- a. CDAI response rate (CR70) and remission rate at week 12 will be analyzed using logistic regression model considering randomization strata (Japanese/Non-Japanese and Male/Female) and treatment group as fixed factor. This model will estimate the Odds Ratio between the treatment arms.

Also, the CDAI response rate (CR70, CR100) and remission rate are also to be described by treatment group week 2, week 4, week 8 and week 12.

And finally, CDAI, change and percentage change from baseline will be descriptively analyzed too by treatment group at baseline, week 2, week 4, week 8 and week 12.

- b. PRO2 response rate (PRO2-CR5, PRO2-CR8) and remission rate at week 12 will be analyzed using logistic regression model considering randomization strata (Japanese/Non-Japanese and Male/Female) and treatment group as fixed factor. This model will estimate the Odds Ratio between the treatment arms.

Also, the PRO2 response rate (PRO2-CR5, PRO2-CR8) and remission rate are also to be described by treatment group week 2, week 4, week 8 and week 12.

And finally, PRO2, change and percentage change from baseline will be descriptively analyzed too by treatment group at baseline, week 2, week 4, week 8 and week 12.

- c. SES-CD endoscopic response rate and endoscopic remission rate at week 12 will be analyzed using logistic regression model considering randomization strata (Japanese/Non-Japanese and Male/Female) and treatment group as fixed factor.
Also, the SES-CD endoscopic response rate and remission rate are also to be described by treatment group week 2, week 4, week 8 and week 12.
And finally, SES-CD endoscopic, change and percentage change from baseline will be descriptively analyzed too by treatment group at baseline, week 2, week 4, week 8 and week 12.
- d. Steroid-free CDAI response rate (CR70, CR100) and remission rate will be described by treatment group at week 2, week 4, week 8 and week 12.
- e. Steroid-free PRO2 response rate (PRO2-CR5, PRO2-CR8) and remission rate will be described by treatment group at week 2, week 4, week 8 and week 12.
- f. The dose of adrenocorticosteroids related to Crohn's disease will be described using the change and percentage change from baseline by treatment group at baseline, week 2, week 4, week 8 and week 12.

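### The plan gives no E6011-minus-placebo difference, interval or baseline adjustment for the CDAI, PRO2 and SES-CD change endpoints, only by-arm summaries with a CI on each arm's own mean

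*SAP*

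**What the plan says.** SAP 4.5.2 lists the change endpoints among the secondary endpoints, for example "Change and percent change in CDAI score from baseline at each evaluation time", with matching entries for PRO2 and, at Week 12, SES-CD.

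SAP 6.8.2 then plans the following:
- CDAI (item a): "CDAI, change and percentage change from baseline will be descriptively analyzed too by treatment group".
- PRO2 (item b): "PRO2, change and percentage change from baseline will be descriptively analyzed too by treatment group".
- SES-CD (item c): "SES-CD endoscopic, change and percentage change from baseline will be descriptively analyzed too by treatment group".

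Protocol 9.7.1.6.2 plans no more than this: "Summary statistics for CDAI value, change and percent change from baseline are also to be calculated by treatment group and evaluation time".

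On intervals, SAP 6.1 says "Changes from baseline will be presented with its 95% confidence intervals". SAP 10 lays all summary tables out by treatment group and race, and gives each quantitative variable with its "mean and its CI (95% level"). SAP 6.8.4, on other efficacy analyses, is marked not applicable.

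On missing data, the default in SAP 10 is "Analysis will be based on observed cases, i.e., no replacement of missing data is planned in general", unless a methods section plans otherwise.

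The dichotomised versions are treated differently. At Week 12, SAP 6.8.2 fits a logistic regression with treatment group and strata to CR70, CDAI remission, the PRO2 responses and remission, and the endoscopic response and remission.

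**The concern.** The primary objective is efficacy shown in a placebo-controlled comparison. For these scores the plan prespecifies a comparison only after they have been cut into yes/no form. The full scores get an interval that answers another question: whether one arm changed from its own baseline.

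That interval is a poor guide to drug effect here. Protocol 9.3.1, criterion 3, admits patients on a Week 0 pre-dose CDAI of 220 to 450 and a PRO2 of 14 to 34, and those same measurements serve as baseline. Regression to the mean and placebo response therefore enter each arm's change, and the placebo interval can exclude zero without any drug effect.

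Protocol 9.7.2 records 25 enrolled patients against 40 planned. Chance imbalance in baseline scores is more likely at that size, so an adjusted estimate is worth fixing in advance. SAP 6.1 permits unspecified exploratory testing and modelling, but a model chosen after unblinding does not carry the same weight.

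**Working it through.** **1. The plan's own figure.** SAP 8 states a probability above 80% of confirming efficacy with 20 per arm and a true CR100 difference of 40 points. Inputs are the rule P(p1 - p2 ≥ 0.25 | data) ≥ 0.50 and Beta(1/2, 1/2) priors (SAP 6.8.1). The placebo rate is not given, so it was varied from 5% to 50%. Exact enumeration gives 0.807 to 0.849, so the figure reproduces. With 25 patients the same rule gives 0.755 to 0.817 (13 E6011, 12 placebo) or 0.752 to 0.808 (12, 13).

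**2. What the planned intervals measure.** The 13/12 split is assumed from 1:1 allocation of 25 patients. The 95% half-widths, in SDs of change, are:
- E6011 arm: 2.179/√13 = 0.60
- placebo arm: 2.201/√12 = 0.64
- difference (not planned): 2.069 × √(1/13 + 1/12) = 2.069 × 0.400 = 0.83

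For an assumed SD of CDAI change of 70 to 100 points, that is about 42 to 64 points per arm and 58 to 83 points for the difference. The intervals shown are narrower than the one that bears on E6011.

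**3. Placebo interval without a drug effect.** Assume 12 placebo patients, normal change and a true placebo CR100 of 20%. The mean reduction is then 100 - 0.842 × SD.
- SD 70: mean 41.1, SE 70/√12 = 20.2, ratio 2.03. The interval lies wholly on the improvement side with probability 46%.
- SD 100: mean 15.8, SE 28.9, ratio 0.55. The probability is 7%.

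**4. Power of a between-arm comparison (two-sided 5%, 13 v 12).** With CR100 of 60% v 20% and a common SD of change, the standardised difference is 0.253 + 0.842 = 1.095.
- Unadjusted: non-centrality 1.095/0.400 = 2.74 on 23 df, power 0.75.
- ANCOVA: divide the non-centrality by √R, where R = (1 - ρ²)/(k² + 1 - 2ρk). Here ρ is the baseline/Week 12 correlation and k is the baseline SD over the Week 12 SD.

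| k | ρ | R | ANCOVA power (22 df) |
|---|---|---|---|
| 1 | 0.2 | 0.60 | 0.92 |
| 1 | 0.6 | 0.80 | 0.83 |
| 0.6 | 0.2 | 0.86 | 0.81 |
| 0.6 | 0.6 | 1.00 | 0.74 |

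The case k = 0.6 stands for eligibility limits that narrow the baseline spread. Adjustment therefore removes between none and 40% of the variance. Two further allocation factors reduce the df to 20 and lower these powers by less than 0.01.

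**5. The planned binary rule at the same setting.** At 13/12 and 60% v 20%, the Bayesian rule succeeds with probability 0.80 (0.79 at 12/13). Its one-sided false-positive rate at 13/12 is 0.048 when both rates are 20% and 0.10 when both are 40%.

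**The case against.** The strongest reply is that this is an exploratory, mainly descriptive plan, that SAP and protocol agree on it, and that the efficacy decision rests on CR100 alone. That stands: it is an analysis weakness, not a contradiction, and the primary conclusion does not depend on it.

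Four stronger readings are tempting, and the documents do not support them.

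- **That the scores receive no randomised comparison.** The tables show both randomised arms side by side with n, mean and SD, so a crude difference and its interval can be worked out. The dichotomised scores are also modelled between arms.
- **That the plan treats a within-arm interval as evidence of efficacy.** No section says so. The sentence in SAP 6.1 does not even say per arm. That follows only when it is read with SAP 6.8.2 and SAP 10.
- **That the continuous scores are far more powerful than the binary endpoint.** A two-sided Fisher test at the setting above has about 50% power, but the trial plans no such test. Against the planned rule, at about 80%, the unadjusted comparison is no better, and ANCOVA runs from somewhat worse to better. The error rates differ as well, and the documents give no SD or correlation.
- **That observed-case means favour the arm losing more failures.** No dropout rate is given. Protocol Table 4 schedules CDAI, PRO2 and colonoscopy at discontinuation, and the day-based windows in SAP 6.6 do not exclude that visit. The direction of any bias is therefore unknown. What does stand is that no missing-data assumption is stated for change scores. NRI is not defined for a continuous score, and the LOCF and observed-case sensitivity analyses cover only the primary endpoint.

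**Conclusion.** The point holds as a gap in prespecification. Three named secondary endpoints have no planned treatment difference, no interval for one and no baseline adjustment. The interval that is planned mixes any drug effect with placebo response and regression to the mean. Subgroup tables by baseline CDAI, PRO2 and SES-CD (SAP 6.1) do not amount to adjustment.

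The size depends on assumptions that the documents cannot settle: the 13/12 split, normal change, CR100 of 60% v 20%, and the values of ρ and k. On those, adjustment may add nothing or may raise power from about 75% to 92%. The calculation covers CDAI only. Nothing in the documents allows one for PRO2 or SES-CD. The case for acting rests on having a prespecified, adjusted estimate at very little cost, not on a power gain over CR100.

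**What to change.** In SAP 6.8.2 a-c, before the remission-induction data are unblinded:

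1. Add an exploratory ANCOVA of Week 12 change for each of CDAI, PRO2 and SES-CD, with arm, the baseline score and the actual allocation factors. Those are Japanese/non-Japanese and previous biologics yes/no (SAP 3.2), not the Male/Female stratum that SAP 6.8.2 names for the logistic models. State a rule for dropping a factor with a sparse level. The protocol expected 8 of 40 patients to be biologic-naive, which is 8/40 × 25 = 5 patients if the proportion held.
2. Report the E6011-minus-placebo difference with its 95% CI next to the descriptive tables.
3. State that the main analysis uses observed Week 12 data, and add one sensitivity analysis for dropouts, for example zero change for patients without a Week 12 score.
4. A repeated-measures model for CDAI and PRO2 at Weeks 2, 4, 8 and 12 is an acceptable alternative if a simple covariance structure is fixed in advance and missing-at-random is stated. An unstructured matrix would need 10 covariance parameters from 25 patients. SES-CD is scheduled only at screening, Week 12 and discontinuation in this period, so ANCOVA is the option there.

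The cost is SAP wording, a few extra models and about three degrees of freedom for covariates. No new data are needed and the primary analysis does not change.
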